1.3 General data handling strategy

1.3.1 Output data precision

Decimal places to be used in displays of demographic, background and duration of exposure variables will be as follows:

- 3 decimal places (p-values; if p-value is less than 0.001, display <0.001),
- 2 decimal places (standard errors and standard deviations),
- 1 decimal place (means, medians),
- 1 decimal place (minimums, maximums),
- 1 decimal place (percentages),
- if percentage = 100, no decimal is required.

Decimal places for efficacy and other safety summary tables and listings will be as follows:

- 3 decimal places (p-values; if p-value is less than 0.001, display <0.001),
- data precision + 2 decimal places (standard errors and standard deviations),
- data precision + 1 decimal place (means, medians),
- same as data precision (minimums, maximums),
- 1 decimal place (percentages),
- if percentage = 100, no decimal is required.

Decimal places for the Hematology, Biochemistry and Urinalysis tables will be as follows:

- 2 decimal places for standard errors and standard deviations (Hematology and Biochemistry), 3 decimal places for standard errors and standard deviations (Urinalysis),
- 2 decimal places for means, medians (Hematology and Biochemistry), 3 decimal places for means, medians (Urinalysis),
- 2 decimal places for minimums, maximums (Hematology and Biochemistry), 3 decimal places for minimums, maximums (Urinalysis).

For vital signs tables of change from baseline, 2 decimal places for mean, median, standard deviation, minimum and maximum will be used.

In outputs containing estimates and p-values for inferential purposes (e.g. ANCOVA), means, standard errors, standard deviations and confidence intervals will be output to 2 decimal places for all parameters. P-values will be output to 3 decimal places; if a p-value is less than 0.001, it will be displayed as <0.001.

1.3.2 Efficacy Assessment Window / Week X Measurement

For all efficacy variables, the measurements obtained at the scheduled visit corresponding to *X* weeks (e.g. 13, 26, ..., 260 weeks) of treatment as defined in the assessment schedule table [Tables 6-1 and 6-2 in the protocol] will be considered as Week *X* measurement (e.g. Week 13, 26, ... , 260 measurements) if $-28 \text{ days} < (\text{visit date} - \text{Week X date}) < 28 \text{ days}$. The Week *X* date is the theoretical date when the visit should have occurred (e.g. if the scheduled visit is

visit 5, corresponding to week 26, then the Week 26 date is the treatment start date + 26 weeks).

Discontinuation visits will be assigned to the closest unallocated visit. For example, if a patient discontinues at visit 4, this discontinuation visit will be re-assigned from visit 777 to visit 4 (and not visit 23). This re-assigned visit value will be stored in a separate variable, i.e. the original value will not be overwritten.

Efficacy data obtained at visits outside the above defined window or at unscheduled visits will be excluded from the analyses and tabulation of summary statistics by visit. However, they will be displayed in the patient data listings. If the last on-treatment observations of the efficacy variables are obtained at a visit outside the above defined windows or at an unscheduled visit, they will still be used for the FAS analysis based on the last observation carried forward (LOCF) imputed endpoint (see [section 1.2](#)).

Note that prior to implementation of these windows, the remapping of the efficacy laboratory parameters will be implemented.

1.3.3 Laboratory visit windows

Safety lab data

The following will be implemented for non-efficacy laboratory data:

- Safety lab data will be summarized and listed as reported on LRS panel, no additional visit windows will be used.
- Laboratory "Visit dates" from the VIS panel on eCRF will not be listed, instead laboratory listings will present the date and day of the sample collection (obtained directly from LRS).

Efficacy laboratory data

The idea of the visit window is to ensure that as many scheduled visits as possible are included in summaries of efficacy parameters over time.

For all *efficacy laboratory summaries over time* (tables and figures), a "re-defined scheduled visit" will be created as follows:

- If scheduled visit laboratory sample already exists on database then that sample remains as the "re-defined scheduled visit".
- If scheduled visit laboratory sample is missing, then search for unscheduled sample closest to actual scheduled visit date (theoretical date visit should have occurred based on treatment start date). If unscheduled sample closest to actual scheduled visit date is within 7 days of actual scheduled date then map this unscheduled visit to the scheduled visit number in the "re-defined scheduled visit". If there is a tie between unscheduled samples before and after the actual visit, take the later measurement. Note that the randomization visit laboratory measurement will not consider measurements from unscheduled visits taken after Day 1.

All efficacy outputs will include the following footnote: *"In the case of a missing scheduled visit sample, the closest unscheduled visit within 7 days of scheduled visit is used."*

1.3.4 Multiple laboratory measurements within same day

It is possible that 2 sets of laboratory measurements may be taken with the sample date. All such measurements will be included in the summaries and listings of notably abnormal or percent change from baseline summaries. For the analysis of “persistent” events (where consecutive measurements are checked) or for the analysis of parameter over time in the following key safety parameters, only the highest within-day value will be included:

- ALT
- AST
- Bilirubin (direct and/or total)
- CPK

Specifically, in the case of duplicate measurements with same sample date, only the maximum value will be selected. All samples will be listed along with sample date.

1.4 Duration of exposure to study medication

Treatment start date is defined as the earliest vildagliptin/placebo date as recorded on the vildagliptin/placebo dosage administration page of the eCRF).

Overall duration (in months) on study medication will be computed as follows:

If a complete last study drug date is available:

$$(\text{last study drug date} - \text{treatment start date} + 1) / 30.4375,$$

or if the last study drug date is missing or incomplete:

$$(\text{last visit date} - \text{treatment start date}) / 30.4375,$$

or if a patient received no dose of randomized double-blind medication:

overall duration is set to 0.

The study drug end date is defined as the last treatment date. The last treatment date in the study completion panel will be used for this study drug end date.

1.5 Treatment-Emergent Adverse Events

A treatment-emerging adverse event is defined as

- an undesirable sign, symptom, or medical condition with onset after the first dose of study medication or,
- an increase in severity of an event that is present during the pre-treatment period,
- all events included on the database will be included in AE summary tables/listings.

1.6 Other clinically significant events (predefined AE risks)

For this project, there are some predefined adverse event risks that are considered of special interest defined as below:

Important identified risks

- Transaminase elevations and Drug-induced liver injury (DILI)
- Angioedema

- Acute pancreatitis
- Skin lesions (pemphigoids)
- Hypoglycemia
- Lactic acidosis (metformin)

Important potential risks

- Serious infections
- Cardiac events in CHF (NYHA Functional Class III) patients (adjudication)
- Muscle events/ myopathy/rhabdomyolysis
- Neuropsychiatric events
- Breast cancer
- Pancreatic cancer

1.7 Hypoglycemic Event Classifications

Patients were educated to record hypoglycemic symptoms and treatment in a study diary. Study diary data were then entered in the Glycemia Study Diary or Adverse Event eCRF, respectively according to the following criteria. The Glycemia study diaries were reviewed by the study staff at each visit and assessed according to [Table 1-1](#). Note that if glucose is recorded as whole blood on the eCRF, rather than plasma, then it will be converted to a plasma value in the derived dataset, using a conversion factor of 1.12 (i.e. plasma glucose = blood glucose x 1.12).

Table 1-1 Recording and classification of glycemia study diary data

Severity	Symptoms	Plasma glucose	Action taken	Classification
Patient able to initiate self-treatment if necessary	Symptoms suggestive of hypoglycemia	< 3.1mmol/L (56mg/dL)	Enter in Glycemia Study Diary eCRF	Hypoglycemic event, grade 1
	Symptoms suggestive of hypoglycemia	≥ 3.1mmol/L(56mg /dL)	Enter in Glycemia Study Diary eCRF	Adverse Event
	Symptoms suggestive of hypoglycemia	Not taken	Enter in Glycemia Study Diary eCRF	Adverse Event
	Asymptomatic	< 3.1mmol/L(56mg /dL)	Enter in Glycemia Study Diary eCRF	Asymptomatic low blood glucose
Patient is unable to initiate self-treatment and requires assistance of another person or hospitalization	Symptoms suggestive of hypoglycemia	< 3.1mmol/L(56mg /dL)	Enter in Glycemia Study Diary eCRF & report as SAE	Hypoglycemic event, grade 2 & SAE
	Symptoms suggestive of hypoglycemia	Not taken	Enter in Glycemia Study Diary eCRF & report as SAE	Suspected hypoglycemic event, grade 2 & SAE

1.8 Laboratory abnormalities

Laboratory data will be presented in SI units only.

1.8.1 Clinically Significant Laboratory Abnormalities

Notable ranges for selected laboratory parameters of interest as listed in [Table 1-2](#) are the basis for the central laboratory to generate notable reports to alert the investigators. The notable ranges will form the basis to evaluate the incidence of clinically significant laboratory abnormalities.

Table 1-2 Notable ranges (absolute) criteria of laboratory variables of specific interest

Lab test description	SI Unit	Notable ranges	
		Low	High
Hematology			
Total leucocytes (WBC)	10E9/L	≤ 2.8	
Total leucocytes (WBC)	10E9/L		≥ 16.0
Platelet count (direct)	10E9/L	≤ 75	
Platelet count (direct)	10E9/L		≥ 700
Hemoglobin	g/L	≤115 (m) ≤ 95 (f)	–
Hematocrit	1	<0.37 (m) ≤ 0.32 (f)	–
Eosinophils	%	–	≥ 14
Biochemistry			
Sodium	mmol/L	≤ 125	
Sodium	mmol/L		≥ 160
Potassium	mmol/L	≤ 3	
Potassium	mmol/L		≥ 6
Blood urea nitrogen (BUN)	mmol/L	–	≥ 14.28
Creatinine	μmol/L	–	≥ 176.8

1.8.2 Hepatic enzyme and CPK elevations

In addition to the notable ranges, the incidence of treatment emergent hepatic enzyme elevations is of interest. These are described in [Table 1-3](#).

Treatment emergent is defined as not meeting the criterion at any pre-baseline visit, but then meeting the criterion at a post-baseline visit. Consequently a patient may be classified treatment emergent ≥5ULN even though they were not classified as treatment emergent ≥3ULN (if had a result ≥3ULN at a pre-baseline visit).

Table 1-3 Treatment emergent hepatic enzyme and CPK elevations of interest

ALT or AST ≥ 3*ULN

ALT or AST \geq 5*ULN
ALT or AST \geq 8*ULN
ALT or AST \geq 10*ULN
ALT or AST \geq 20*ULN
ALT or AST \geq 3*ULN and Bilirubin[^] \geq 1.5*ULN
ALT or AST \geq 3*ULN and Bilirubin[^] \geq 2*ULN
Bilirubin[^] \geq 2*ULN
Bilirubin[^] \geq 3*ULN
CPK \geq 5*ULN
CPK \geq 10*ULN
ALT \geq 3*ULN
ALT \geq 5*ULN
ALT \geq 8 x ULN
ALT \geq 10*ULN
ALT \geq 20*ULN
ALT \geq 3*ULN and Bilirubin[^] \geq 1.5*ULN
ALT \geq 3*ULN and Bilirubin[^] \geq 2*ULN
AST \geq 3*ULN
AST \geq 5*ULN
AST \geq 8 x ULN
AST \geq 10*ULN
AST \geq 20*ULN
Alkaline Phosphatase \geq 1.5*ULN

[^] If only direct bilirubin is measured then direct bilirubin will be used for all criteria involving bilirubin. If both total and direct bilirubin are measured (i.e. are in the laboratory specifications) throughout a study, total bilirubin will be preferred. The clinical study team has agreed that total bilirubin should be used for this study. Note that if at any visit total bilirubin has not been measured then the elevation will not be assessed for that visit (even if direct bilirubin has been measured).

In addition to the overall summary of elevations defined above, the same criteria will also be presented, restricted to “persistent elevations” only. Persistent elevations are those which meet the criterion at consecutive on-treatment measurements or at last on-treatment visit (this includes assessments within one day of the last dose of study treatment). The purpose of the persistent definition is to remove transient elevations from the summary (i.e. those elevations which appeared at one visit but normalized at the next visit).

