 - acute or chronic liver disease, evidence of hepatitis, cirrhosis or portal hypertension.
 - history of imaging abnormalities that suggest liver disease (except hepatic steatosis), such as portal hypertension, capsule scalloping, cirrhosis.
4. Any of the following significant laboratory abnormalities as assessed at Visit 1:
 - a. Clinically significant thyroid stimulating hormone (TSH) outside of the normal range.
 - b. Renal dysfunction defined as calculated creatinine clearance $<60\text{ml}/\text{min}/1.73\text{m}^2$ via modified diet in renal disease (MDRD) formula.
 - c. Alanine aminotransferase (ALT) and/or aspartate aminotransferase (AST) $> 2 \times$ upper limit of normal (ULN) at Visit 1, confirmed by repeat measure within 3 working days.
 - d. Total bilirubin $> 2 \times$ ULN and/or direct bilirubin $> 1 \times$ ULN confirmed by repeat measure within 3 working days.
 - e. Positive Hepatitis B surface antigen (HbsAg).
 - f. Positive Hepatitis C antibody test (anti-hepatitis C virus (HCV)).
 - g. Elevated fasting triglycerides (TGs) $>500\text{mg}/\text{dL}$.
 - h. Clinically significant laboratory abnormalities which, in the opinion of the investigator, cause the patient to be considered inappropriate for inclusion in the study.
5. Any of the following electrocardiogram (ECG) abnormalities at Visit 1:
 1. Second or third degree atrio-ventricular block without a pacemaker.
 2. Long QT syndrome or corrected QT $>500\text{ms}$.
6. Previous or current participation in any vildagliptin clinical study.
7. History of hypersensitivity to any of the study drugs or to drugs of similar chemical classes.

8. Concurrent medical condition that may interfere with the interpretation of efficacy and safety data during the study.
9. Donation of ≥ 500 mL or more of blood, significant blood loss equaling to at least one unit of blood within the past 2 weeks or a blood transfusion within the past 8 weeks.
10. Potentially unreliable and/or those judged by the investigator to be unsuitable for the study.
11. Use of an investigative drug within 30 days or 5 half-lives of the drug, whichever is longer.
12. Inability to comply with the study procedures or medications.

No additional exclusions may be applied by the investigator, in order to ensure that the study population will be representative of all eligible patients.

5 Treatment

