1.1 Baseline definitions

Unless specified otherwise, the baseline will be the measurement obtained on Day 1, or the closest sample obtained at an earlier visit (scheduled or unscheduled) to Day 1, if the Day 1 measurement is missing.

For derived variables [REDACTED] the baseline will be derived using measurements obtained on Day 1, or the closest samples obtained at an earlier visit (scheduled or unscheduled) to Day 1, if the Day 1 measurements are missing. Details of imputation methods to use if one or more of the individual measurements used in the derivation is missing, are detailed in [section 2.2.3.1](#).

Day 1 will be defined as the first day of study treatment (the earliest vildagliptin/placebo date as recorded on the vildagliptin/placebo dosage administration page of the eCRF).

Vital Signs

For blood pressure and pulse, baseline will be defined as the average of all pre-treatment visits, regardless of being scheduled or unscheduled. For [REDACTED], baseline will be defined as the day 1 measurement if non-missing, or last non-missing value coming from either an earlier scheduled or unscheduled visit.

Routine ECG Measurements

ECGs are analyzed and interpreted locally for this study, hence only qualitative ECG measurements are recorded. ECGs are scheduled to be measured at screening (and not Day 1). Baseline is therefore defined as the measurement obtained at screening, unless there is a later, unscheduled measurement on or before Day 1 (in which case the latest of these will be used).

[REDACTED]

[REDACTED]

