2.3.2 Laboratory values

The details of laboratory parameters collected, SI units (note, only SI units will be reported), and normal ranges will be listed in [Section 16 of CSR](#). Note that lipid parameters are summarized along with other biochemistry laboratory parameters. Meal test laboratory parameters (glucose, insulin and c-peptide) are for use in efficacy analyses only and so should not be included in safety laboratory outputs.

Notable ranges (absolute) criteria of selected laboratory variables are defined in [Section 1.8](#) above. The laboratory values to be considered for notable ranges or relevant changes will include all post-baseline values up to the final scheduled visit, including values at unscheduled visits prior to the last visit. Only treatment emergent notable abnormalities will be considered (i.e. notably abnormal measurements which were not present at any pre-baseline visit). In addition to summary tables, a listing of patients with any treatment emergent notable laboratory results during the treatment period will be provided by treatment approach and patient number, along with their values at all visits, including repeated, unscheduled and follow-up laboratory values. In the listing, all abnormal values outside of normal range and notable values will be flagged, e.g., L/H for a value being below/above normal range, LN/HN for a value being in notable low/high range.

For each numerical laboratory parameter, the laboratory values will be reported in listings to the same precision as that for the unit in UNITCONV dataset. The precision to use in tables is as per [Section 1.3.1](#).

For continuous variables with a value <lower limit, these will be imputed as being half of the lower limit. For continuous variables with a value >upper limit, these will be imputed as being equal to the upper limit.

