2.3.2.2 Biochemistry

The values of biochemistry laboratory test results at baseline and endpoints (End of Period 1, End of Period 2, End of Study) will be summarized, as well as the changes from baseline to each endpoint.

The maximum/minimum value obtained during the treatment period, and the change from baseline to maximum/minimum value will be summarized by treatment approach for each hematology parameter.

The number and percentage of patients with abnormal biochemistry test results meeting notable criteria post-baseline, which were not present prior to randomization, will be tabulated. This summary will be repeated for abnormalities occurring in Period 1.

The number and percentage of patients with hepatic enzyme elevations (defined in [Table 1-3](#)), and persistent hepatic enzyme elevations will be presented, and the patients meeting any of the criteria will be listed. Note that for this study total bilirubin will be used for all criteria involving bilirubin. If at any visit total bilirubin has not been measured then the elevation will not be assessed for that visit (even if direct bilirubin has been measured).

The liver panel A testing data for patients with hepatic enzyme elevations will be listed at patient level. Liver panel B testing data will not be considered as part of the RAP, but will be included in narratives if applicable.

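### The treatment-emergent laboratory rule never checks the pre-dose Day 1 baseline sample, so some elevations that began before randomised treatment are counted as treatment-emergent

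*SAP*

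**What the plan says.** The wording discussed here is the same in SAP V3.0 and in Addendum 1.

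- **Hepatic and CPK elevations (SAP 1.8.2, Table 1-3).** "Treatment emergent is defined as not meeting the criterion at any pre-baseline visit, but then meeting the criterion at a post-baseline visit". The section adds an example: a patient may count as treatment-emergent at 5 x ULN but not at 3 x ULN, because of a pre-baseline result of at least 3 x ULN.
- **Notable-range tests (SAP 2.3.2, Table 1-2).** Only treatment-emergent abnormalities count, described as "notably abnormal measurements which were not present at any pre-baseline visit".
- **Tabulation of the notable-range tests (SAP 2.3.2.1 and 2.3.2.2).** Here the condition is different: abnormalities "which were not present prior to randomization". The hepatic summary in 2.3.2.2 does not carry this condition. It refers to Table 1-3 and so to the 1.8.2 rule.
- **Baseline (SAP 1.1).** Unless specified otherwise, "the baseline will be the measurement obtained on Day 1", or the closest earlier sample if that is missing. Day 1 is the first day of vildagliptin or placebo.
- **Order of events at a visit (Protocol 5.5.4).** Study medication is taken after that visit's procedures are complete.
- **Entry limits (Protocol 4.2).** ALT and/or AST above 2 x ULN "at Visit 1, confirmed by repeat measure within 3 working days" is an exclusion, as is confirmed total bilirubin above 2 x ULN or direct bilirubin above 1 x ULN.

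**The concern.** A treatment-emergent filter should remove abnormalities that were already there before the randomised drug was started. The most informative sample for this is the last one before dosing, which is the Visit 3 sample, taken after any metformin run-in. As worded, the rule screens visits before baseline and counts visits after it, and says nothing about baseline itself.

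Transaminase elevation and drug-induced liver injury head the list of important identified risks in SAP 1.6. Liver-enzyme and CPK elevations, including persistent ones, are named key safety variables in SAP 2.3. If a pre-dose elevation is reported as treatment-emergent, the incidence shown for these variables is too high. SAP 1.5 ties treatment-emergent adverse events to onset or worsening after first dose; the laboratory rule departs from that principle.

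**Working it through.** The plan states no figure on this point, so the check sets the definitions against the visit schedule.

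**Step 1: which samples exist.** In Protocol Table 6-1, standard chemistry is scheduled at Visit 1 (week -5) and Visit 3 (baseline), then at Visits 7 and 11. The liver-only panel starts at Visit 4. So Visit 1 is the only scheduled pre-baseline chemistry and Visit 3 is the baseline. If the Day 1 sample is missing, the closest earlier sample becomes baseline. In the absence of unscheduled tests that is Visit 1, and no pre-baseline chemistry remains.

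**Step 2: all patterns of criterion met (1) or not met (0).**

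| Visit 1 | Visit 3 (pre-dose) | Post-baseline | Treatment-emergent as worded | Treatment-emergent if baseline is screened too |
|---|---|---|---|---|
| 0 | 0 | 0 | no | no |
| 0 | 0 | 1 | yes | yes |
| 0 | 1 | 0 | no | no |
| 0 | 1 | 1 | **yes** | **no** |
| 1 | 0 | 0 | no | no |
| 1 | 0 | 1 | no | no |
| 1 | 1 | 0 | no | no |
| 1 | 1 | 1 | no | no |

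Exactly one of the eight patterns is classified differently: absent at Visit 1, present at Visit 3, present again later.

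**Step 3: what the Visit 1 filter can remove.** Compare the Table 1-3 thresholds with the entry limits.

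- ALT and/or AST at 3, 5, 8, 10 and 20 x ULN: all lie above the 2 x ULN exclusion limit. The criteria combining ALT/AST with bilirubin also need at least 3 x ULN.
- Bilirubin at 3 x ULN: above the limit. Bilirubin at 2 x ULN: a value of exactly 2.0 x ULN is both eligible and at the criterion.
- For these tests, apart from that boundary value, the filter acts only on a Visit 1 value not confirmed on repeat, a protocol deviation or an unscheduled pre-baseline sample.
- CPK and alkaline phosphatase have no specific numeric entry limit, so Visit 1 can screen out patients for them. The baseline gap in step 2 applies to them all the same.

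**Step 4: whether another step catches the pattern.** Protocol 6.2 bases laboratory eligibility on Visit 1 samples, so a Visit 3 elevation does not by itself stop randomisation. Protocol 6.5.5 calls for repeat testing when a Table 6-4 liver criterion is met, and SAP 2.3.2 admits unscheduled post-baseline values. Early retests therefore make a second positive value more likely to be recorded. The persistent-elevation summary removes transient rises, but a lasting pre-existing rise would pass it.

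**Step 5: size, on assumptions only.** Let q be the share of patients who meet a criterion at Visit 3 but not at Visit 1, and r the share of those who meet it again later. Neither is in the documents. Reclassified patients = N x q x r, with N = 2000 (1000 per arm, Protocol 9.6):

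- q = 0.1%, r = 30%: 2000 x 0.001 x 0.3 = 0.6
- q = 0.5%, r = 50%: 2000 x 0.005 x 0.5 = 5
- q = 1%, r = 80%: 2000 x 0.01 x 0.8 = 16

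Per 1000 patients the range is 0.3 to 8.

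**The case against.** The strongest reply is that *pre-baseline* is loose wording for pre-treatment. SAP 2.3.2.1 and 2.3.2.2 cut at randomisation for the tests that 2.3.2 governs, and the 3 x ULN example in 1.8.2 would be almost impossible if it meant Visit 1 alone, given the entry limits. This is plausible, and a reader should not infer that the authors deliberately chose to disregard Day 1. But a programmer works from the wording, and 1.8.2 as written omits the sample.

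Three stronger readings are tempting and are not supported:

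- *Any abnormality present at baseline counts as treatment-emergent.* It does not. The criterion must also be unmet at Visit 1 and met again post-baseline. For ALT/AST this usually means a rise from no more than 2 x ULN to at least 3 x ULN within the screening and run-in weeks. That window is shorter for patients already on at least 1000 mg metformin, who go directly to randomisation (Protocol 3.1.1).
- *The liver table is built under two conflicting rules.* It is not. Only 1.8.2 governs it. The conflict between 2.3.2 and its subsections concerns the Table 1-2 tests, which include no ALT, AST or bilirubin.
- *A hepatic signal would be hidden.* Adding equal numbers to both arms does shrink a ratio: 20 against 10 (2.0) becomes 25 against 15 (1.67), although the difference stays at 10. Those counts are invented, however. With 0.3 added per arm, the low end of step 5, the ratio is 20.3/10.3 = 1.97. No between-arm test of these elevations is planned; SAP 2.3.2.2 gives numbers and percentages, and the only safety test specified is the Period 1 hypoglycaemia chi-square.

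It is also true that baseline values are summarised, along with changes from baseline, and that patients meeting a hepatic criterion are listed. This limits the loss but does not correct the incidence table.

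**Conclusion.** The point holds for the wording. SAP 1.8.2 and 2.3.2 leave the Day 1 pre-dose sample unchecked, and one visit pattern is misclassified as a result. For ALT/AST and bilirubin the remaining filter removes very few patients. That is an inference from the entry criteria, not a count in the documents, and it does not extend to CPK or alkaline phosphatase. Separately, the notable-range tests are given two different conditions that need to be reconciled.

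The consequence is a modest inflation of descriptive incidence in both arms. Treating it as non-differential assumes that baseline elevations, and their recurrence, are similar between arms. The documents do not allow the size to be derived; the 0.6 to 16 of 2000 rests entirely on the assumed q and r. The efficacy analyses, including the primary endpoint, are not touched.

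**What to change.** In SAP 1.8.2 and 2.3.2, replace *at any pre-baseline visit* with *at baseline (Day 1, pre-dose) or any earlier visit*. Change the 3 x ULN example in 1.8.2 to match. Use the same words in 2.3.2.1 and 2.3.2.2 in place of the condition on randomisation, so that the listing and the tables identify the same patients.

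The cost is one phrase in each section and one condition in the derivation program. No new data are needed, because the Visit 3 chemistry and hematology are already collected.
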